The secondary aim of this study is to assess the effects of 12-weeks of endurance exercise training on WAT-specific IR and fasting FFA levels and molecular adaptations in skeletal muscle that may contribute to the alterations in WAT.

Approach: Blood samples and dialysates from abdominal subcutaneous WAT will be collected during hyperinsulinemic clamp to assess whole-body IR and WAT-specific suppression of lipolytic rates under physiological insulin in men and pre-menopausal women with obesity. A skeletal muscle biopsy from the vastus lateralis will be collected before and after 12 weeks of deuterium (2H) labelled water administration and endurance exercise training to assess transcriptomic and proteomic adaptation that may associate with WAT adaptations.

Study Design

Research Design

This is a double-site (AH TRI and PBRC), longitudinal (12 weeks) randomized clinical trial with two groups; a control group (CTRL) and an exercise training group (EX)

Research Intervention Description

Subjects will be submitted to 12 weeks of supervised aerobic exercise training intervention and oral deuterium-labelled water administration OR oral deuterium-labelled water administration only.

This study consists of a Screening Period, Baseline Period, Intervention Period, and Follow-up Period, detailed below.

Study Site(s)/Location(s) and Number of Subjects

AdventHealth Orlando Sites: Translational Research Institute (TRI)

Estimated number of subjects at AdventHealth Orlando site: 35 men and women (accounting for a 20% dropout; we expect 29 to complete the study)

Name of external site(s) outside of AdventHealth Orlando: Pennington Biomedical Research Center

Estimated number of subjects at external sites: 35 men and women (accounting for a 20% dropout; we expect 29 to complete the study)

Total number of all sites: 2

Estimated number of subjects at all sites combined: 70

Multi-Site Research Logistics/Communication Plan

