Waiver or Alteration of the Consent Process (consent will not be obtained, required information will not be disclosed, or the research involves deception)

N/A

Waiver or Alteration of HIPAA Authorization

Partial waiver of HIPAA authorization will be requested.

Non-English Speaking Subjects

We intend to enroll only English-speaking participants due to the complexity of the study procedures and the lack of translational capacity that could be adequately provided throughout the duration of the study.

Randomization

Men and women will be randomized to the CTRL and EX groups on a 1:1 basis following successful completion of the VO₂max test and imaging tests. Participants will be stratified by sex to ensure balance between each of the groups. Stratifying allows for different sample sizes in each sex, but ensures that within each sex, there are an equal number of treatments and controls.

Study Visits

Study visits will be conducted at the AdventHealth Translational Research Institute or Pennington Biomedical Research Center.

Screening Visit (SV) (Outpatient; Approximate visit time: 2 hours)

Participants will arrive for this outpatient visit after a 10 hour overnight fast. After obtaining informed consent, data collection for assessing eligibility will commence. The screening visit will include:

¹Urine for pregnancy test (if applicable), urinalysis, and toxicology screen (Amphetamine, Barbiturate, Benzodiazepine, Cocaine, Methadone, Opiate, THC, Cannabis, Tricyclics, and Oxycodone)

²Demographics and complete medical history (including, but not limited to, alcohol use, concomitant medications, health conditions, allergies and exercise habits)

³Vital signs (respiratory rate, temperature, heart rate, blood pressure)

⁴Standard physical examination performed by a study physician, physician assistant, or nurse practitioner

⁵Anthropometrics including height, weight, waist circumference, and BMI

⁶Screening blood draw to measure CBC with differential and platelets, comprehensive metabolic panel (CMP), lipid profile, blood glucose, HbA1C, ALT, AST, alkaline phosphatase, insulin level, and TSH

⁷Electrocardiogram (ECG)

⁸Consent Process Checklist assessing the potential participants' understanding of and willingness to perform all study activities.

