The participant will be contacted by phone within 24-72 hours after baseline visit 2 discharge to ensure no adverse events have occurred on both biopsy and arterial line sites.

Intervention Period (Weeks 1-12)

Biopsy and catheter insertion site check: A biopsy site and catheter site check will be done when the participants pick up their first supply of ${}^{2}H_{2}O$.

H₂O Administration and Return (12-week labelling period) and Urine Collections: ²H₂O will be prepared by the Mass Spectrometry Core. Participants will receive 50 mL aliquots of 70% ²H₂O or 35 mL aliquots of 99.9% ²H₂O in individual amber prescription containers. Participants will drink three 35 mL or 50 mL doses per day for the first week, and two doses per day from the second through the twelfth week. Participants will receive the ²H₂O aliquots containers bi-weekly, a log sheet to record consumption, and at-home urine collection cups with instructions. Participants will be instructed to keep urine samples taken at home in the refrigerator until their next in-person visit (every other week). Urine samples will be used to verify compliance weekly (at AH TRI or PBRC). Compliance with ²H₂O intake for both groups will be monitored through the weekly urine collections and return of empty containers for counting. ²H enrichments in urine, reflecting ²H body water enrichments, will be measured by isotope ratio mass spectrometry. Enrichments are expected to be between 1-2.5%. If a participant's urine sample is <1%, the study team will encourage compliance with the participant. If enrichment is <1% for a period of 3 weeks, the PIs will discuss participant withdrawal. Participants will be instructed to maintain their normal daily and weekly routines.

Participants in the EX group will engage in 12-week endurance exercise training.

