The TRI facility will be the main repository for biospecimen samples. PBRC will ship all tissue and blood samples (with exception of WAT samples needed for triglyceride turnover and adipocyte formation analysis and screening/safety visits) to AH TRI for testing and storage. The AH TRI will ship WAT samples needed for triglyceride turnover and adipocyte formation analysis. Material Transfer Agreements will be in place prior to transferring any samples between study sites. The MTA will govern the transfer and chain of custody of biospecimens outside of AdventHealth.

Current Version Date: 08/05/2024 IRBNet #: 1805407
Page 26 of 42

The adipose tissue specimens and plasma/serum samples will be stored indefinitely, or until a sample is fully used. All biological specimens will be stored without identifiers or linkage codes.

After study aims have been achieved and study related endpoints have been measured and analyzed, any remaining biospecimens will be stored at the TRI Laboratory Room 2404 and will then be considered as "archived biospecimens." Archived biospecimens will be used for any additional hypothesis-related experimentation or testing for the purposes of this study, consistent with the original aims, which cannot be predicted at the time the protocol is developed due to the evolving nature of scientific exploration.

Additionally, archived biospecimen samples may be stored indefinitely for future research. Archived biospecimens could be used for separate research by both
AdventHealth and PBRC scientists and scientists outside of AdventHealth and PBRC. This would be allowed for research of any type (without limitation to disease, process, or research methods) if it has scientific merit as determined by the PI, with an additional review by the respective Program Director. For research outside of AdventHealth or PBRC, a Material Transfer Agreement will be obtained, which will govern the transfer and chain of custody of the biospecimens outside of AdventHealth or PBRC.

Study Outcome Measures (Endpoints)

Primary outcomes:

- 1. In vivo adipogenesis in WAT. New adipocyte formation will be assessed two times (pre and post intervention) on the frozen isolated ²H₂O labelled adipose tissue cells.
- 2. In vivo TG turnover. WAT TG turnover rates will be assessed two times (pre and post intervention) on abdominal subcutaneous WAT on the extracted lipid from the frozen ²H₂O labelled adipose tissue.

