The primary aim is powered to detect differences in the change in *in vivo* formation of new adipocytes (i.e., fraction of newly formed adipocytes; "f") of subcutaneous WAT between the CTRL and EX groups. We hypothesize that the EX-group will have a decrease in the fraction of newly formed adipocytes in response to the EX intervention as compared to the CTRL group. Analysis of women from our previous VIVA study (NCT03530111) indicates that the mean value of "f" in the physically active (exercise) group is 11.4%, while the sedentary group has an "f" value of 17.8%. Because VIVA only has crosssectional data (assessment at one time-point), we must also use data from the Apple & Pear study (NCT01748994) 9 to estimate the change in fraction of newly formed adipocytes, as the proposed study includes an exercise intervention. By utilizing data from the CTRLgroup in the Apple & Pear study 9 (baseline assessment) and increasing the estimate to ensure that the study is well-powered, we can estimate the CTRL and EX groups from the proposed study to have an overall mean "f" value of 17% (at baseline) with a standard deviation of 6.0%. A total sample size of 58 (assuming a ~17% overall lost-to-follow-up rate) will provide at least 80% power to detect significant differences in "f" between the CTRL and EX groups, with a 5% significance level.

Current Version Date: 08/05/2024 IRBNet #: 1805407
Page 29 of 42

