Single nuclei RNAseq Power Calculation. To date the most comprehensive analysis of human WAT has been conducted by Emont and colleagues who performed snRNAseq in whole frozen WAT and VAT from humans with obesity and established 17 subpopulations of cells. However, these data were generated using the 10X Genomics platform. We have published preliminary snRNAseq data in WAT from 22 individuals with overweight and obesity. We expect to capture nuclei from the WAT that may reveal up to 12 different cell populations (Fig. 4). If we assume the rarest cell type is 2% and require at least a 100 of the of rarest cell type to accurately quantify and describe it, we require a total of 6,792 nuclei to achieve a 99% probability of meeting these requirements. Our current technique permits 1400 cells per participant to be analyzed which equates to 28,000 cells for 20 participants at each timepoint in EX-group and 14,000 nuclei for 10 participants at each timepoint in the CTRL-group. This would allow us to accurately define subpopulations within WAT and generate sufficient data to compare the impact of endurance exercise on adipocyte populations and non-adipocyte populations.

Statistical Analysis Plan

Primary and Secondary Objective Analysis

Shapiro-Wilk test will be initially performed to assess the normality of data and homogeneity of variances. Pre- and post-intervention results will then be tested by paired t-test or Wilcoxon signed-rank test, as appropriate. Results will be expressed as mean \pm standard deviation and significance will be established, *a priori*, at p≤0.05.

Potential Risks and Benefits

Potential Benefits

The potential benefits to an individual participant in this study are not known. Exercise training can trigger many beneficial adaptations, but individual responses and adaptations vary. All participants will acquire knowledge about their physiological status (e.g., cardiorespiratory fitness, body composition, etc.) that may be of personal benefit. The risks presented to participants are minimal, and information gained from this project will be useful to identify mechanisms responsible for exercise effects on adipose tissue quality and insulin resistance in subjects with obesity.

Potential Risks

Described below are all the known risks of being in this study.

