Appendix:

The following table identifies the procedures in relation to the study timeline for CTRL group:

	Screen	В	aseline						² H:	2O Inter	vention	Period					F	Follow-	-up	
					Week															
Visits	SV1	V1	V	2	1	2	3	4	5	6	7	8	9	10	11	12	V3	V	4 §	
Days		-14	-8	-7	0-6	7-13	14-20	21-27	28-34	35-41	42-48	49-55	56-62	63-69	70-76	77-83	85	87	88	
Windows	Within 28 days of V1	±2	±2		±1	±1	±1	±1	±1	±1	±1	±1	±1	±1	±1	±1	±1	±1		
Informed Consent	X																			
Eligibility Assessment	X																			
Randomization		X																		
Urine Collection (urea, nitrogen and creatinine)			X															X		
Urine Collection (pregnancy, if applicable)	X	X							X								X			
Urine Collection (toxicology)	X																			
Physical Exam + Medical History	X																			
Vital Signs	X																			
Anthropometrics	X	X															X			
Screening Blood Draw	X																			
Electrocardiogram	X																			
Surveys			X															X		
MRI		X															X			
DEXA		X							X*								X			
VO2max Test		X															X			
Overnight Stay with Standardized Meal			X															X		
7-Day Food Record Start				X												X				
7-Day Food Record Return					X												X			
Hair Collection			X															X		
WAT Biopsy				X															X	
Muscle Biopsy				X															X	
Respiratory Quotient (Hood)				X															X	
Pre-Clamp Blood Draw				X															X	

Hyperinsulinemic-euglycemic Clamp + Microdialysis				X															X
Accelerometer Provided			X													X			
Biopsy and Catheter Insertion Site Check					X														X
On-site Body Weight Measurement							X		X		X		X		X				
Weight Maintenance and Health Education							X		X		X		X		X				
² H ₂ O Pick-up					X		X		X		X		X		X				
² H ₂ O Container Return							X		X		X		X		X	X			
² H ₂ O Urine Collection					X	X	X	X	X	X	X	X	X	X	X	X			
Review Adverse Events	X	X	X	X	X	X	X	X	X	X	X	X	X	X	X	X	X	X	X

^{*}DEXA can take place between Weeks 4-6 to increase scheduling flexibility

On-site Body Weight Measurement, Weight Maintenance and Health Education, and ²H₂O activities must occur on the first day of exercise for that week.

[§]Visit 4 procedures must be done within 36-48 hours after the VO2max test

The following table identifies the procedures in relation to the study timeline for EX group:

The following table identifi	Screen		Baseline						H ₂ O and		_	ention P	eriod				Fo	llow-u	-up
			Week																
Visits	SV1	V1	V	2	1	2	3	4	5	6	7	8	9	10	11	12	V3§	V	7 4

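### The protocol tests only pre versus post within participants, although the trial is randomised and sized to compare exercise with control

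*Protocol*

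**What the plan says.** The protocol's section Statistical Analysis Plan, under Primary and Secondary Objective Analysis, starts with a Shapiro-Wilk check and continues: "Pre- and post-intervention results will then be tested by paired t-test or Wilcoxon signed-rank test, as appropriate". Significance is set at p≤0.05. It does not say whether the paired test is run in each arm or on both arms together. No two-sample test, ANCOVA, mixed model or group-by-time term appears here or elsewhere in the document.

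Other sections describe a comparison of two arms:

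- **Randomization:** "Men and women will be randomized to the CTRL and EX groups on a 1:1 basis", stratified by sex.
- **Sample Size Determination, hypothesis:** a "decrease in the fraction of newly formed adipocytes in response to the EX intervention as compared to the CTRL group".
- **Sample Size Determination, power:** 58 participants give at least 80% power for a difference in f "between the CTRL and EX groups, with a 5% significance level".

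Three further statements bear on what a pre/post test would measure:

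- **Study Outcome Measures:** "New adipocyte formation will be assessed two times (pre and post intervention"; triglyceride (TG) turnover is handled in the same way.
- **Baseline Visit 2 and Intervention Period:** the pre biopsy is on Day -7. The labelled water comes later: "A biopsy site and catheter site check will be done when the participants pick up their first supply of" it, in Week 1.
- **Appendix, footnote to the CTRL schedule:** "Visit 4 procedures must be done within 36-48 hours after the VO2max test". The EX schedule carries the same interval.

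**The concern.** The named test answers a different question from the one the trial was designed and sized for. A paired test asks whether a value moved between two visits. The hypothesis asks whether it moved differently under exercise than under control. Run in EX alone, the paired test makes no use of the control arm. Run on the pooled participants, it mixes the two arms. Comparing one arm's p-value with the other's is not a test of the difference either.

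Any shift common to both arms would then be read as an effect of exercise. The document contains two plausible sources of such a shift:

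- **Label-derived outcomes (f and TG turnover).** The first biopsy is taken before any labelled water is drunk and the second after 12 weeks of it. The appearance of label is common to both arms.
- **Clamp outcomes.** The nominal gap from VO2max test to clamp is 7 days at baseline (Day -14 to Day -7). At follow-up it is about 3 days by the visit days (Day 85 to Day 88), or 36–48 hours by the footnote. The two follow-up statements should be reconciled, but both are shorter than the nominal baseline gap, and in both arms.

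A between-arm comparison removes whatever part of such a shift is equal in the arms. A paired test removes none of it.

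**Working it through.** All tests are taken as two-sided at 5% (the protocol does not state sidedness). Paired and two-sample power come from the non-central t distribution.

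**1. Which contrast gives 58?** Inputs from Sample Size Determination: f of 17.8% (sedentary) and 11.4% (active), SD of f 6.0%, total 58, so 29 per arm. The protocol gives neither an SD of change nor a pre–post correlation.

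- Difference: 17.8 − 11.4 = 6.4 points.
- SD of change = 6.0 × √(2(1 − ρ)). With ρ = 0 (assumed) this is 8.49.
- A two-sample t-test at 80% power needs 28.6 per arm, so 29 per arm and 58 in total. Power is 80.6% with 29 per arm and 79.2% with 28.
- With SD 6.0 used directly, 14.8 per arm are needed, so 30 in total, which does not match.

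The stated 58 is thus reproduced by a between-arm comparison of change with ρ = 0. This agrees with the section's own words.

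**2. Outcomes with a real baseline, no exercise effect, same shift in both arms.** The non-centrality of the paired test is (shift / SD of change) × √n. The shifts are assumptions.

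| Shared shift (SD of change) | Paired, EX only, n = 29 | Paired, pooled, n = 58 | Between arms |
|---|---|---|---|
| 0.1 | 8% | 12% | 5% |
| 0.2 | 18% | 32% | 5% |
| 0.3 | 35% | 61% | 5% |
| 0.4 | 55% | 85% | 5% |
| 0.5 | 74% | 96% | 5% |

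**3. f, if the unlabelled pre sample reads near zero (assumed).**

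- No exercise effect, both arms ending at 17% with SD 6%: 17/6 = 2.83. The paired test is significant in over 99.9% of trials in each arm; a between-arm test is significant in 5%.
- Exercise effect as in the protocol's source figures: 11.4/6 = 1.90 in EX and 17.8/6 = 2.97 in CTRL. Both paired tests are again significant in over 99.9% of trials, and both as a rise. With an SD of 12 in EX, 11.4/12 = 0.95 still gives over 99%.
- A between-arm t-test of the post values, 17.8 versus 11.4 with SD 6 and 29 per arm, has 97.9% power.

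The paired result therefore looks the same with or without an exercise effect.

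**4. f, if it does have a real baseline, no exercise effect, same shift in both arms (assumed).** EX paired test, n = 29:

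| Shared shift in f | SD of change 6 (ρ = 0.5) | SD of change 8.49 (ρ = 0) |
|---|---|---|
| 1 point | 14% | 9% |
| 2 points | 41% | 23% |
| 3 points | 74% | 45% |

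Setting per-arm p-values side by side does not help. With a 2-point shift and SD 6, EX is significant and CTRL is not in 0.41 × (1 − 0.41) = 24% of trials without any exercise effect.

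These figures do not cover the snRNAseq outcomes, which are planned on 20 EX and 10 CTRL participants.

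**The case against.** The analysis paragraph does not exclude a group comparison. The power statement implies one, and the planned check of homogeneity of variances makes sense for two groups but not for a paired test. A separate SAP might name the model. This makes it likely that a between-arm analysis was intended. It does not supply one: a power target is not an analysis method, and Shapiro-Wilk tests normality, not equality of variances. Nor is this a detail left open for the SAP. The protocol itself names the test for both sets of objectives, and a correct SAP would have to depart from it.

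The objections to the illustrations have more force:

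- The shared shifts have no source in the document. At 0.1 or 0.2 SD the excess is modest.
- The protocol gives 6.0% as the SD of f at baseline, not of its change. With 8.49 the figures for f fall to 9%, 23% and 45%, and between-arm power for the change is 81%. The 98% applies to a comparison of post values, for which an SD of f is the apt input.
- The protocol gives 17% as a baseline value. Using it as the level reached after labelling is an assumption, and an unlabelled baseline is also a problem of endpoint definition in its own right.
- Nothing in the document shows that the VO2max test alters the clamp at these intervals. With the ±2-day windows at Visits 1 and 2 the baseline gap could shrink to about 3 days.

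These points limit how precisely the harm can be stated. None makes a paired test estimate EX minus CTRL.

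**Conclusion.** The concern holds and must be fixed. The test named for the primary and secondary objectives does not address the protocol's own hypothesis, and this is so even if nothing drifts in either arm. The mismatch itself rests on no numerical assumption.

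The size of the harm does depend on assumptions. For outcomes with a real baseline, a shared shift of 0.3 to 0.5 SD of the change turns a nominal 5% error into 35% to 74% in EX alone and 61% to 96% pooled. For f, if the pre biopsy carries no label, the paired test is close to certain to be significant in both arms and says nothing about exercise.

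**What to change.** Replace the sentence on paired tests with wording such as:

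> The primary analysis of each primary and secondary outcome compares EX with CTRL, with participants analysed in their assigned arm. Where a meaningful baseline exists, the post value is analysed by ANCOVA adjusted for baseline and sex (the randomisation stratum). For label-derived outcomes whose pre sample precedes labelling, the post value is compared between arms, adjusted for sex. The adjusted EX minus CTRL difference is reported with its 95% confidence interval. Paired pre/post tests are descriptive only.

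A group-by-time mixed model adjusted for sex would serve in place of ANCOVA, but one model should be named as primary. The snRNAseq outcomes may need their own model; the requirement there is that it compares the arms.

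Align Study Outcome Measures and Sample Size Determination with this, since both now describe f as a pre/post quantity or a change. Correct the Shapiro-Wilk sentence, which assigns it a check of variances. Adjustment for site and a rank-based sensitivity test are optional.

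The cost is protocol wording. The total of 58 stands: with a difference of 6.4 points, 29 per arm give 81% power for change at ρ = 0 and 98% for the post value at SD 6. No new participants, visits or data are needed.

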Using a suite of innovative methods, ours will be the first study to comprehensively assess the direct effects of exercise on features of WAT quality both in vivo (formation of new adipocytes and adipocyte TG turnover) and ex vivo (cellular landscape of WAT) and WAT-specific IR (suppression of lipolysis via subcutaneous microdialysis) in humans with obesity. Using a practical approach of isotopic labeling that incorporates deuterium (2H), administered as oral 2H2O, into the DNA and TG moieties of adipocytes, we have compelling published and preliminary evidence that exercise reduces in vivo formation of new adipocytes in both mice and humans, suggesting an important exercise-induced mechanism of WAT remodeling [3-5]. We reason that increased adipocyte TG turnover rates improve adipocyte function, WAT-specific IR and overall WAT quality and thus abrogate the need for increased formation of new adipocytes.

Adipocytes comprise 90% of the tissue volume, but only ~50% of WAT cellular content, with the remainder comprised of immune cells, stem cells, and pre-adipocytes [6, 7]. Using our established method [8], we will employ innovative single nuclei transcriptomics (snRNAseq) to discover the effects of exercise on senescence and inflammation within adipocytes and non-adipocytes of WAT to further understand how exercise impacts WAT quality and WAT-specific IR via in vivo microdialysis during insulin suppression.

Study Objectives

The overall aim of this study is to investigate the effects of exercise training on adipogenesis, TG turnover and cellular composition of adipose tissue, and insulin resistance in subjects with obesity.

Primary Objective/Aim/Goal/Hypothesis

The primary aim of this study is to investigate the effects of 12-weeks of endurance exercise training on *in vivo* formation of new adipocytes, TG turnover rates, and cellular composition of the WAT.

Approach: A subcutaneous WAT biopsy from the abdomen will be collected before and after 12 weeks of deuterium (2H) labelled water administration and endurance exercise training in men and pre-menopausal women with obesity. Collected WAT samples will be utilized for *in vivo* measurements of adipocyte formation and TG turnover. The remaining WAT samples will be frozen for future analyses that include snRNAseq and histology to assess cellular composition, senescence, and inflammation of the WAT

Secondary Objective/Aim/Goal/Hypothesis

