- 3. Cellular composition of WAT. Cell composition and gene expressions in WAT will be assessed two times (pre and post exercise intervention) by snRNAseq on the frozen adipose tissue.
- 4. Adipocyte morphology, senescence, and inflammation. Adipocyte size, markers of cellular senescence and inflammation will be assessed two times (pre and post exercise intervention) by immunohistochemistry on the formalin-fixed paraffin-embedded adipose tissue.

Secondary outcomes:

1. Whole body and WAT-specific insulin resistance: Whole-body insulin resistance and WAT-specific antilipolytic sensitivity to insulin will be evaluated pre and post exercise intervention *in vivo* using blood and dialysate samples collected during glucose clamp and subcutaneous microdialysis.

Data Management and Quality Plan

Data De-identification

Participants will be enrolled and assigned a participant identification number (PID). This PID is a code consisting of a combination of numerals and letters, which serves as the identifier for this participant for this research study and links them back to their hospital medical record and their protected health information (PHI). Access to the "link" between the PIDs, the PHI, and to the clinical data are only granted to the clinical research team as assigned on the Delegation of Authority Log. All the clinical research and survey data is recorded in a de-identified fashion onto our paper source documents and/or electronic case report forms (CRF). Both sites will enter data into REDCap, a HIPAA-compliant, web-based forms and survey platform approved for use by AdventHealth. REDCap will be used for storage and to facilitate analysis. All data not entered into REDCap (e.g., data collected from individual exercise sessions) will be stored on a shared OneDrive folder only accessible to the assigned study-specific research team at PBRC and AH TRI.

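### Primary outcome 3 (cell composition) is covered only by a within-arm paired test; on cell-type shares, a change in adipocytes shifts every other share

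*Protocol*

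**What the plan says.** Under Study Outcome Measures (Endpoints), the third primary outcome is the cellular composition of white adipose tissue: "Cell composition and gene expressions in WAT will be assessed two times (pre and post exercise intervention) by snRNAseq".

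The Statistical Analysis Plan section has one subsection on inference, headed "Primary and Secondary Objective Analysis". After a normality check its rule is: "Pre- and post-intervention results will then be tested by paired t-test or Wilcoxon signed-rank test, as appropriate", with results given as mean and standard deviation and a 5% level. It makes no exception for outcome 3 and names no analysis variable for it.

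Three other statements bear on the point:

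- The single-nuclei power paragraph says: "We expect to capture nuclei from the WAT that may reveal up to 12 different cell populations". It describes the rarest type by a percentage (2%).
- The same paragraph caps the reading: "Our current technique permits 1400 cells per participant to be analyzed", with 20 EX and 10 CTRL participants at each timepoint.
- The Background Information and Scientific Rationale section gives adipocytes 90% of tissue volume "but only ~50% of WAT cellular content".

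**The concern.** With a capped number of nuclei per sample, the counts carry relative information only. If one type takes a larger share, the others must together take a smaller one. A separate paired test on each share treats the types as free to move independently, so a response in adipocytes alone can appear as significant falls in immune, stem and stromal populations whose numbers did not change.

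The single-nuclei data are meant to show how exercise affects adipocyte and non-adipocyte populations, and the induced shift lies on exactly that contrast. The stated test also looks only within an arm. A shift over 12 weeks in the exercise group is then never set against the randomised controls, although Sample Size Determination frames the primary aim as a difference in change between CTRL and EX.

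**Working it through.** **The plan's own figure.** The 6,792 nuclei are meant to give a 99% chance of at least 100 nuclei of a 2% type. The smallest n with P(Binomial(n, 0.02) ≥ 100) ≥ 0.99 is 6,224 for one such type. Requiring it jointly for 12 types gives 6,703, and for 20 types exactly 6,792. The figure is therefore about right, but it concerns detecting a type and says nothing about the test.

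**Inputs from the protocol.** Up to 12 types, adipocytes about 50%, rarest type 2%, 1,400 nuclei per participant, 20 EX and 10 CTRL.

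**Inputs assumed, because the protocol gives none.** Fold change in adipocytes; within-person log SD 0.2 to 0.4; between-person log SD 0.3; the other 11 types between 2% and 10%, rescaled to total 50%.

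**Step 1: the exact shift.** If a type with share p changes by fold f, every other share is multiplied by 1/(1 + (f − 1)p).

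- p = 0.5, f = 1.2: 1/1.10 = 0.909, a 9% fall.
- p = 0.5, f = 1.5: 1/1.25 = 0.80, a 20% fall.
- p = 0.5, f = 0.7: 1/0.85 = 1.176, an 18% rise.
- p = 0.02, f = 1.5: 1/1.01 = 0.990, a 1% fall.

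For an unchanged 2% type, 1,400 × 0.02 = 28 expected nuclei become 28/1.1 = 25.5 when adipocytes rise by 20%. The difference is small in one sample but goes the same way in every EX participant.

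**Step 2: how often an unchanged type is flagged.** Multinomial simulation, only adipocytes changing and only in EX, within-person log SD 0.2. Mean rejection per unchanged type at 5%:

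| Adipocyte nuclei in EX | Paired t on shares | Between-arm t on shares | Between-arm t, log-ratio to sample median |
|---|---|---|---|
| no change | 5% | 5% | 5% |
| +20% | 18% | 9% | 4–5% |
| +50% | 65% | 26–28% | 5% |

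Repeat runs differ by one or two points. The Wilcoxon test behaves like the t-test.

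**Step 3: sensitivity.**

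- At a within-person log SD of 0.4 the paired rates drop to about 8% (+20%) and 25% (+50%).
- At 0.5 the +20% case gives 7% paired and 6% between-arm.
- With other settings (between-person log SD 0.4, within-person CV 0.2 to 0.5), a 50% type rising by half gives 59% to 18% paired; a 50% type falling by 30% gives 41% to 12%.
- If only a 2% type rises by 50%, the rate stays at 5%.

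**Step 4: what the between-arm contrast does.** Controls do not change on average, so the expected induced shift is the same in both tests. The rate falls because the standard error grows: √(1/20 + 1/10) against √(1/20), a ratio of √3 = 1.73. The contrast therefore reduces the flags without removing the cause.

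**Step 5: limits of the log-ratio.** The median log-ratio holds 5% above because most types are unchanged there. When 7 of 12 types fall by 30%, it flags unchanged types about 43% of the time, against 12% to 22% for the between-arm test on shares.

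**The case against.** The analysis sentence is a one-line general rule. It mentions neither cell composition nor shares, and a paired test on log-ratios would comply with it. A reader might infer that the protocol prescribes type-by-type tests of raw shares. It does not say so; that is the natural reading of percentages reported as mean and standard deviation, but still an inference. A separate statistical analysis plan could define the variable. This stands, and it limits the point to a conditional one. It does not remove it, because the protocol is not silent on the test and what it fixes is a within-arm comparison.

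Composition is a relative quantity. When adipocytes go from 50% to 54.5% (0.6/1.1), the other shares really do fall by 9%, and a test on shares reports this correctly. This stands too: the error lies in reading the fall as loss of cells. The protocol does not say which meaning is intended.

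A reader might also infer that any real change in one cell type produces false changes in the rest. The protocol's own figures do not support that: the size depends on how abundant the changing type is, and for a 2% type it is negligible.

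Finally, the chance that at least one of 11 unchanged types is flagged (85% at +20%) looks dramatic, but it is already 41% with no effect at all. Much of it is multiplicity, so it is not used as the measure of this problem.

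**Conclusion.** The point holds in a conditional form. The only stated test for primary outcome 3 is a within-arm paired test, and if it is run on shares, a change in adipocytes alone will make unchanged types appear to move. The 9% shift at +20% adipocytes is exact arithmetic from the 50% share. The flag rates (about 18% to 8% at +20%, about 65% to 25% at +50%) rest on assumed within-person log SDs of 0.2 to 0.4, on adipocytes alone changing, and on the 20 EX participants of the single-nuclei subset.

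It would go too far to conclude that shares must be abandoned for a log-ratio, since the usual log-ratio to the sample median does worse when several types move together. Given the interest in inflammation and senescence, such broad change is plausible. Nor does the finding touch the sizing of the trial, which rests on the fraction of newly formed adipocytes. It merits correction before the single-nuclei data are analysed.

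**What to change.** For primary outcome 3:

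1. Replace the paired within-arm test with the between-arm difference in change from baseline, with the participant (not the nucleus) as the unit. This is the randomised comparison and matches the between-group aim in Sample Size Determination.
2. State that cell-type shares are relative and are not to be read as absolute gain or loss of cells.
3. Report a compositional analysis (log-ratio or count model) beside the shares. State its reference assumption: which type is taken as unchanged, or that most types are. Do not make a log-ratio to the sample median the sole analysis.

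The cost is a few sentences, slightly more analysis work, and power. With 20 EX and 10 CTRL and an assumed within-person CV of 0.3, power to detect a 50% rise in adipocytes falls from about 96% (paired, within EX) to about 62% (between-arm); at a CV of 0.2 it falls from about 100% to 89%. The within-arm figure is not a fair benchmark, because that test does not estimate the effect of randomised exercise against control.
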